ABG	arterial blood gas
AE	adverse event
AKI	acute kidney injury
AKIN	Acute Kidney Injury Network
ALF	acute liver failure
CFR	Code of Federal Regulations
CRF	case report form
CRRT	continuous renal replacement therapy
CTSI	Clinical & Translational Science Institute
DCD	donor after cardiac death
DMC	Data Monitoring Committee
DNDD	donor after neurologic determination of death
EBL	estimated blood loss
ECD	esophageal cooling device
ELISA	enzyme-linked immunosorbent assay
EMR	electronic medical record
FDA	Food and Drug Administration
FFP	fresh frozen plasma
GCP	Good Clinical Practice
GI	gastrointestinal
HIPAA	Health Insurance Portability and Accountability Act of 1996
ICA	International Club for Ascites
ICF	informed consent form
ICU	intensive care unit
IEC	Independent Ethics Committee
I-R	ischemia-reperfusion
IRB	Institutional Review Board
IVC	inferior vena cava
ITT	intention-to-treat
LTx	liver transplantation
NGAL	neutrophil gelatinase-associated lipocalin
OG	orogastric
PI	Principal Investigator
pRBC	packed red blood cells
RCT	randomized controlled trial
RRT	renal replacement therapy
SAE	serious adverse experience

sCR	serum creatinine

- **SSI** surgical site infection
- TEE transesophageal echocardiography

PROTOCOL SYNOPSIS

TITLE	Mild Hypothermia to Prevent Acute Kidney Injury in Liver Transplantation (MHALT)	
SPONSOR	University of California, San Francisco	
FUNDING ORGANIZATION	Department of Anesthesia and Perioperative Care	
NUMBER OF SITES	3	
RATIONALE	Patients undergoing liver transplantation (LTx) are at extremely high risk of perioperative acute kidney injury (AKI). AKI has enormous impact on outcomes and cost after LTx. 68% of patients at UCSF sustain some degree of AKI and 12% develop AKI Stage 3 (a three- fold increase in sCr from baseline or need for dialysis) after LTx. Thirty-day and 1-year mortality, graft survival, and progression to chronic kidney disease correlate with the presence and severity of AKI. Clearly, any intervention that reduces the incidence or severity of AKI in this population would have tremendous impact on short and long-term outcomes and cost. This trial will study mild hypothermia in LTx for prevention of AKI. The protocol is based on strong preliminary data from rodent studies showing that hypothermia protects renal function in ischemia- reperfusion models. Recent work from our department has shown that mild hypothermia in deceased organ donors improves graft function after kidney transplantation. In light of these preliminary data, we propose a trial of mild hypothermia to prevent AKI in LTx.	
STUDY DESIGN	This is a single-blind, randomized controlled trial	
PRIMARY OBJECTIVE	Assess whether or not mild hypothermia has a protective effect on early AKI after liver transplantation.	
SECONDARY OBJECTIVES	 Demonstrate the feasibility of mild hypothermia during liver transplantation. Assess whether or not mild hypothermia reduces early biomarkers of AKI during liver transplantation such as neutrophil gelatinase-associated lipocalin (NGAL) 	
NUMBER OF SUBJECTS	230	
SUBJECT SELECTION CRITERIA	Inclusion Criteria: 1. Age ≥ 18 years 2. LTx from a donor after neurologic determination of death (DNDD) Exclusion Criteria: 1. LTx from a donor after cardiac death (DCD) 2. LTx for acute liver failure (ALF) 3. Living-donor LTx 4. Simultaneous liver-kidney transplantation	

	5. Preoperative renal replacement therapy (RRT)	
	6. Preoperative intubation and/or mechanical ventilation	
	7. Portopulmonary hypertension	
TEST TREATMENT	Mild hypothermia (34-35 °C) during liver transplantation	
AND METHOD OF		
ADMINISTRATION	Mild hypothermia will be induced using an esophageal cooling device	
	(ECD), as well as standard measures after the induction of general	
	anesthesia until blood flow is completely restored to the liver. The	
	anticipated median duration of mild hypothermia will be 4-5 hours.	
	When feasible, the right kidney will also be packed with ice-cold	
	sponges to enhance cooling of the renal parenchyma during the	
	anhepatic phase of the operation.	
CONTROL	Normothermia (36.5-37.5 °C) during liver transplantation	
TREATMENT AND	romotiona (50.5 57.5 °C) during irver dunsplanation	
METHOD OF	Normothermia will be maintained using an ECD as well as standard	
ADMINISTRATION	measures after the induction of general anesthesia and throughout the	
	liver transplant operation.	
	Subjects will be on study for up to one year.	
DURATION OF	Screening: less than 1 day	
SUBJECT PARTICIPATION	Treatment: less than 1 day (during liver transplantation)	
	Follow-up: 1 year	
AND DURATION OF	The total duration of the study is expected to be 36 months. 24	
STUDY	months for subject recruitment and 12 for final subject follow-up.	
CONCOMMITANT	Allowed: N/A	
MEDICATIONS	Allowed. N/A	
MEDICATIONS	Prohibited: N/A	
FEELCACY		
EFFICACY EVALUATIONS		
PRIMARY ENDPOINT	Incidence of acute kidney injury within 72 hours after liver	
TRIMARI ENDI OINT	transplantation	
SECONDARY	 Distribution of the stages of acute kidney injury within 72 hours 	
ENDPOINTS	after liver transplantation	
	 Duration of intensive care unit stay 	
	 Duration of hospital stay 	
	 One-year survival rate 	
	 Need for renal replacement therapy within 7-days, at 30-days, and 	
	at 1 year after transplant	
	 Persistent renal dysfunction at 90-days and 1-year after transplant 	
	 Change in serum NGAL levels from baseline to 2 hours after 	
	reperfusion of the portal vein	
	 Change in urine NGAL levels from baseline to 2 hours after 	
	reperfusion of the portal vein	
OTHER	Percentage of intraoperative time within target temperature range	
EVALUATIONS	i i oreentage of intraoperative time within target temperature range	
LIALUAIIUNS	 	

SAFETY EVALUATIONS	 Time to reach normothermia upon initiation of re-warming (mild hypothermia arm) Number of units of blood products transfused (packed red blood cells, fresh frozen plasma, platelets, and cryoprecipitate) Incidence of surgical site infections within 2 weeks of LTx Intraoperative vasopressor doses
PLANNED INTERIM ANALYSES	When 50% of patients have completed the study, an interim analysis for efficacy will be conducted by an independent data safety monitoring board (DSMB).
STATISTICS Primary Analysis Plan	Presence or absence of AKI, and the different categories of AKI (Stage 1, 2, or 3 or no AKI), will be summarized as frequency and percentage. The primary outcome (presence or absence of AKI) will be compared between the two arms by a two-sample proportion test. The frequency of different categories of AKI (Stage 1, 2, or 3 or no AKI) will be analyzed by a chi-square test. Intention-to-treat analysis will be performed.
Rationale for Number of Subjects	The incidence of AKI in LTx patients at UCSF is 68%. Considering one interim analysis for efficacy, we estimate a sample size of 101 subjects per arm is needed to detect a 30% reduction in AKI with 80% power at overall $\alpha = 0.05$ (two-tailed). To allow for approximately 10% study drop-out or inability to complete the study protocol, we plan to enroll a total of 230 subjects.

1 BACKGROUND

This trial proposes a mild hypothermia intervention (34-35 °C) that is pragmatic, simple, and non-invasive. Cooling will be performed using an Esophageal Cooling Device (ECD) model EnsoETM (Attune Medical) as well as standard measures (forced-air blankets, conductive table cooling). The ECD is a Food and Drug Administration (FDA) approved device that is placed in a manner identical to a standard orogastric (OG) tube.¹⁻³ The ECD will help maintain the core temperature of the anesthetized patient between 34-35 °C during LTx. This temperature range is only slightly lower than that typically seen in LTx due to passive heat loss. When possible, the surgeon will also apply local cooling (ice-cold sponges on the surgical field) to the right kidney during the anhepatic phase of the operation. After blood flow is fully restored to the liver, the ECD and standard measures (forced-air, fluid, and table warmers, plus a heated anesthesia circuit) will be used to actively rewarm subjects.

1.1 Overview of Non-Clinical Studies

Extensive rodent work by [name], one of the investigators for the current trial, and colleagues has shown the benefits of mild hypothermia for protecting visceral organs against ischemia-reperfusion (I-R) injury. Prior work showed that mild hypothermia (33-34 °C) is protective against hepatic ischemic injury in both obese and lean rats.⁴⁻⁷ In soon to be published rodent work, [name] group has shown that mild hypothermia also protects the kidney from injury and inflammation induced by renal artery clamping. Other researchers have also shown that mild-moderate hypothermia reduces acute kidney injury due to I-R.⁸

1.2 Overview of Clinical Studies

Therapeutic hypothermia has long been investigated as a way to preserve end-organ function from ischemic insult, by reducing oxygen consumption, free radical production, and inflammation.⁹ Targeted temperature management has been recommended to preserve neurologic function after cardiac arrest¹⁰ (although recent data has questioned this finding)¹¹ and during circulatory arrest for aortic arch repair.¹² Cold renal perfusion may reduce AKI during open aortic aneurysm repair.¹³ Recently, [name] group has also shown that mild hypothermia in brain-dead organ donors improves graft function after kidney transplantation.¹⁴

The ECD is a US FDA approved device for induction and maintenance of hypothermia through a minimally invasive approach.² The device has been shown to be effective and safe for induction and maintenance of hypothermia after out-of-hospital cardiac arrest¹ and in a series of intensive care unit (ICU) patients.³.

2 STUDY RATIONALE

As in the general hospitalized population, AKI has enormous impact on outcomes and cost after surgery. Numerous, mostly pharmacologic interventions (e.g., dopamine, *N*-acetylcysteine), have been investigated for renal-protecting properties in high-risk surgery - and none have shown clear benefit.^{15,16} Most of these studies suffer from heterogeneous

populations (i.e., a mix of cardiac, vascular, and other high-risk surgery), imprecise definitions of AKI, and a lack of good biomarkers. Patients undergoing LTx are a specific population at extremely high risk of perioperative AKI. Thirty-day and 1-year mortality,¹⁷⁻²⁰ as well as graft survival,^{21,22} correlate with the presence and severity of AKI. While modern surgical technique (partial inferior vena cava cross-clamp) reduces the incidence of AKI,^{23,24} 68% of patients at UCSF sustain some degree of AKI and 12% develop AKI Stage 3 (a three-fold increase in sCr from baseline or need for dialysis) after LTx. Clearly, any intervention that reduces the incidence or severity of AKI in this population would have tremendous impact on short and long-term outcomes and cost.

Given the preliminary data from pre-clinical and clinical studies described above (see Section 1.1 and 1.2), there is good rationale for a trial of mild hypothermia during LTx as a strategy to prevent AKI. The ECD, an FDA-approved device for cooling or warming of patients through a minimally invasive approach, will facilitate rapid cooling of patients to target temperature (test treatment), maintenance of normothermia (control treatment), and re-warming of patients prior to extubation (test treatment). Without the ECD, the current standard-of-care measures for intraoperative temperature control (forced air blankets, conductive table heater/coolers, fluid warmers, and a heated-humidified anesthesia circuit) are unable to achieve the precision needed for this trial.

2.1 Risk / Benefit Assessment

As described above, AKI leads to worse outcomes for patients. The severity of AKI, even after adjustment for multiple cofounders, correlates with increased mortality, hospital length of stay, and \cos^{25} Even AKI Stage 1, characterized by increases in sCr as small as 0.3-0.4 mg/dL, is associated with a 70% increase in risk of death. In cases where sCr rises $\geq 2 \text{ mg/dL}$, the odds ratio for mortality approaches 50 and excess costs exceed \$20,000 per patient. After liver transplant surgery in particular, AKI has enormous impact. Thirty-day and 1-year mortality, as well as graft survival, correlate with the presence and severity of AKI (see above Section 2 for references).

Given the major negative outcomes associated with AKI after liver transplantation, the potential benefit of a positive result in this study is extremely high. Preventing or reducing the severity of AKI in any given participant would clearly result in direct benefit by lowering the risk of outcomes such as mortality, re-hospitalization, graft loss, or chronic kidney disease. The results of the study will help define optimal care for future liver transplant patients, and possibly for other surgical patients at high risk of AKI (e.g., vascular and cardiac surgery). For society at large, a positive result of this trial would likely result in significant monetary savings in terms of health care costs and resource utilization. By comparison, the risks of the study are mild and include (1) risks of the ECD and (2) side effects of hypothermia.

Even though it is removed at the end of surgery, it is possible that placement of the ECD could lead to more discomfort, sore throat, or difficulty swallowing due to the larger size of the device compared with a standard OG tube. However, the ECD is smaller and softer than a transesophageal echo (TEE) probe that is routinely placed during LTx. The

incidence of painful swallowing after TEE insertion is 0.1%,²⁶ and the risk of discomfort after ECD placement is expected to be even lower. To minimize the risk of discomfort, ECDs will be well-lubricated and only placed by study doctors experienced in the placement of OG tubes and TEE probes (attending liver transplant anesthesiologists). While placement of the ECD could theoretically cause gastrointestinal bleeding from varices, placement of larger probes for TEE is generally considered safe during LTx and routinely performed by 86% of liver transplant anesthesiologists in the US.^{27,28}

Mild intraoperative hypothermia has few potential risks.²⁹ Currently 23% of patients experience temperatures < 35 °C during LTx at UCSF (data not shown), although not in a precisely controlled fashion as proposed in this trial. Hypothermia can exacerbate coagulopathy and increase transfusion requirements, but this is mainly described at temperatures below our proposed range of 34-35 °C. Increased bleeding was NOT seen in a large randomized controlled trial (RCT) of cooling to 33 °C in intracranial aneurysm surgery.³⁰ Nevertheless, to mitigate the risk of coagulopathy from hypothermia, the attending liver transplant surgeon will be asked to rate the degree of coagulopathy on a qualitative scale at various points in the operation (see below). If mild hypothermia is felt to be contributing to a coagulopathy that is unsafe for the patient, either the attending surgeon or anesthesiologist may request abortion of the hypothermia protocol at any point in the operation and rewarming of the patient will be initiated. Cardiovascular instability was not observed in a secondary analysis of the aneurysm trial mentioned above³¹ or in the trial of brain-dead kidney donors.¹⁴ Hypothermia has been reported to increase surgical site infections and bacteremia,^{29,30} but we are confident that this can be prevented by active warming prior to case end and the current antibiotic protocols for LTx.

3 STUDY OBJECTIVES

3.1 Primary Objective

The primary objective is to assess whether or not mild hypothermia has a protective effect on early AKI after liver transplantation. We hypothesize that mild hypothermia will protect against intraoperative AKI during LTx. We will measure the proportion of patients that develop AKI in the early post-transplant period (≤ 72 hours) as our primary efficacy outcome. This time window is likely to reflect AKI occurring due to intraoperative events,^{22,32} and therefore has potential to be modulated by the study intervention. Serum creatinine measurements will be recorded by observers blinded to the treatment arm, and the presence and severity of AKI adjudicated according to the latest criteria.^{33,34}

3.2 Secondary Objectives

The secondary objectives are:

• Assess the feasibility of a mild hypothermia protocol during LTx. Cooling will be performed using an ECD as well as standard measures. When possible, the surgeon will also apply local cooling (ice-cold sponges on the surgical field) to the right kidney during the anhepatic phase of the operation. After blood flow is fully

restored to the liver, the ECD and standard measures will be used to actively rewarm subjects. Feasibility will be assessed by the proportion of patients successfully completing the protocol, and the percentage of time spent within the target temperature range.

 Measure biomarkers of AKI during and after mild hypothermia or normothermia in LTx. NGAL, a protein elevated in AKI,³⁵ has been described by [name] group as an early biomarker of AKI during LTx.²⁴ Serum NGAL indicates glomerular injury, while urine NGAL is a marker of distal tubular injury.³⁶ Blood and urine samples will be collected for NGAL determination at baseline and two hours after reperfusion of the portal vein.

4 STUDY DESIGN

4.1 Study Overview

This is a multi-center, single-blind, RCT. 230 subjects are planned. Each subject will have an ECD placed after induction of general anesthesia and undergo LTx with one of two temperature management protocols (Fig. 1). Each subject will receive only one of the two experimental treatments. Subjects will be randomizaed to one of the two treatments. Evaluations will be taken at baseline, and at several intraoperative time points. Data from the electronic medical record will be analyzed post-operatively.

Screening data will be reviewed to determine subject eligibility. Subjects who meet all inclusion criteria and none of the exclusion criteria will be entered into the study.

The following treatment regimens will be used (Fig. 1):

- Experimental treatment Mild hypothermia (34-35 °C). Cooling will be initiated after induction of anesthesia and maintained throughout the anhepatic phase of LTx (Fig. 1). In all feasible cases the surgeon will cover the peritoneal surface over the right kidney, which is exposed during the operation, with ice-cold sponges to enhance cooling of the renal parenchyma. Shortly (15 minutes) after the portal vein is reperfused, the ECD and other standard measures (forced-air, fluid, and table warmers, plus a heated anesthesia circuit) will be used to actively rewarm the patient (expected warming rate ≥ 1 °C/hour). The goal is to achieve normothermia by case end.
- **Control** Normothermia (36.5-37.5 °C). After induction of anesthesia, the ECD and standard warming measures will be used to maintain normothermia throughout the operation.

Total duration of subject participation will be approximately 6-10 hours, which is the duration of surgery. Subjects will be followed up remotely via the electronic medical record (EMR) for 1 year after LTx.

[figure not shown]

Figure 1. Scheme of overall study design showing temperature management protocols.

5 CRITERIA FOR EVALUATION

5.1 Primary Efficacy Endpoint

The primary efficacy endpoint is the incidence of AKI within 72 hours after LTx. The International Club for Ascites (ICA) 2015 criteria, a revision of the KDIGO criteria for patients with cirrhosis, will be used to define AKI.³³ The definitions are as follows:

- AKI: increase in sCr \ge 0.3 mg/dL within a 48 hour time window, or a percentage increase \ge 50% from baseline, or initiation of RRT.
- **Baseline sCr**: the most recent value of sCr prior to LTx

A predefined subgroup analysis of the primary outcome will be performed in patients undergoing liver transplantation for hepatocellular carcinoma (HCC) with Model for Endstage Liver Disease exception points.

5.2 Secondary Efficacy Endpoints

- A. The distribution of the stages of AKI within 72 hours after liver transplantation. The ICA 2015 criteria will be used to define the stages of AKI as follows:
 - AKI Stage 1: increase in sCr ≥ 0.3 mg/dL, or an increase in sCr ≥ 1.5-fold and ≤ 2-fold from baseline.
 - **AKI Stage 2**: increase in sCr > 2-fold and \leq 3-fold from baseline.
 - AKI Stage 3: increase in sCr > 3-fold from baseline, or sCr \ge 4.0 with an acute increase of \ge 0.3 mg/dL, or initiation of RRT
- **B.** Duration of intensive care unit (ICU) stay.

- AKI may worsen volume overload, electrolyte abnormalities, and metabolic acidosis, all of which can lead to prolongation of ICU stay.
- **C.** Duration of hospital stay.
- **D.** One-year survival rate.
 - AKI after LTx is a negative predictor of mortality.^{17,20}
- **E.** Incidence of post-operative renal replacement therapy within 7-days, at 30-days, and at 1 year after transplant.
 - LTx is a predictor of developing chronic renal failure.³⁷
- F. Persistent renal dysfunction at 90-days and 1-year after transplant.
 - Presence of a reduction in GFR by ≥ 25 mL/min or ≥ 50% from baseline (Kellum et al.)
 - We are aware that patients may not have lab values available from dates exactly 30-days, 90-days, and 1-year after the date of transplantation surgery. In order to standardize our data collection, we have developed rules to determine the appropriate serum creatinine values to record. The rules are as follows:

1 year follow up: preferences (in order of preference) for selecting serum creatinine value to record:

- 1. Serum creatinine value within 1 month after 1-year follow-up date.
- 2. Serum creatinine value within 1 month before 1-year follow-up date.
- 3. Serum creatinine value collected at a date after 1-year follow-up date that is beyond 1 month but closest to the follow-up date.

30 and 90 day follow up:

- The serum creatinine value recorded must have been collected on or post the 30 and 90 follow-up dates. Select the serum creatinine value on or closest to the 30- and 90-day follow-up dates.
- **G.** Change in serum NGAL levels from baseline (start of surgery) to 2 hours after reperfusion of the liver graft (opening of the portal vein).
 - NGAL has been shown to be an early marker of AKI in LTx,²⁴ and as such has the potential to be modulated by the study intervention
- **H.** Change in urine NGAL levels from baseline (start of surgery) to 2 hours after reperfusion of the liver graft (opening of the portal vein).
 - NGAL has been shown to be an early marker of AKI in LTx,²⁴ and as such has the potential to be modulated by the study intervention

5.3 Safety Evaluations

A. Intraoperative coagulopathy assessment – while it is unlikely that mild hypothermia (34-35 °C) will significantly impair the coagulation cascade or platelet function to a significant degree,³⁰ we will ask the attending surgeon to qualitatively rate the degree of clinical coagulopathy as visualized on the

abdominal wall at two intraoperative time points: (1) shortly after incision when the abdominal wall retractors are first placed, and (2) 30 minutes after reperfusion of the hepatic artery. Coagulopathy will be rated as minimal, mild, moderate, or severe.

- **B.** Blood product transfusions and estimated blood loss While previous studies of mild hypothermia during intracranial aneurysm surgery did not show increases in surgical bleeding or blood product transfusions,³⁰ we will record the number of packed red blood cell (pRBC), fresh frozen plasma (FFP), platelet, and cryoprecipitate units transfused during surgery, as well as the volume of autologous cell salvage blood (i.e. "Cell Saver", which is standard practice at UCSF in LTx operations) administered to the patient. The estimated blood loss (EBL) will be calculated by the Cell Saver technician and recorded.
- **C. Vasopressor doses** Prior studies of mild intraoperative hypothermia have not shown increased vasopressor requirements,³¹ and vasopressor use is extremely common during LTx. As a safety evaluation, we will record the total vasopressor doses in the pre-anhepatic, anhepatic, and reperfusion phases of LTx.
- **D.** Arterial blood gases The acid-base status of the patient undergoing LTx, as measured by the base deficit on arterial blood gas (ABG) analysis, reflects the overall perfusion of the patient as well as function of the liver graft. ABGs are typically drawn at several time points during the LTx operation and these values will be recorded.
- E. Incidence of the following adverse events (AEs):
 - Significant bleeding in conjunction with evidence of severe, refractory coagulopathy
 - Defined as significant bleeding that is not attributable to vascular injury in the presence of ongoing severe clinical coagulopathy despite aggressive treatment (fresh frozen plasma 15 mL/kg, cryoprecipitate 10 units x 2 doses, and the administration of antifibrinolytics). While coagulopathy is a clinical diagnosis during LTx, we would consider persistent INR > 4 or fibrinogen < 75 mg/dL after the aggressive treatment above as laboratory evidence of severe coagulopathy.
 - Severe upper gastrointestinal (GI) bleeding at the time of ECD insertion
 - It is common to have mild upper GI bleeding after insertion of a standard orogastric tube during liver transplant, so only blood return of > 500 mL will be considered an AE.
 - Severe hypothermia
 - \circ < 33 °C for greater than 30 minutes
 - Oropharyngeal, dental, or esophageal trauma
 - Perforation or damage to the ECD
 - Intraoperative cardiac arrhythmias requiring treatment ³¹ excluding bradycardia typically seen at the time of reperfusion of the liver graft.

- Intraoperative myocardial ischemia or infarction.
- Discomfort (oropharyngeal pain, dysphagia, odynophagia) patients will be asked about these symptoms post-operatively
- Surgical site infections (SSIs) prior to discharge from the hospital after LTx, or within two weeks of LTx (whichever comes first).³⁸

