8.2 Blinding

Due to the objectives of the study, the identity of test and control treatments will not be known to patients. The following study procedures will be in place to ensure single-blind administration of study treatments.

Access to the randomization code will be strictly controlled. The randomization code will not be revealed until the patient has entered the operating room for liver transplantation. The study protocol will be completed in its entirety while the patient is in the operating room under general anesthesia. Therefore, it will be impossible for the patient to know the treatment assignment until the protocol is complete.

No attempt will be made to blind the study doctors (anesthesiologists), who are investigators in the study, to the treatment assignment, as they will be the ones administering and monitoring the temperature protocol during LTx.

Research staff assigned to adjudicate the Primary Outcome (presence or absence of AKI within 72 h of LTx) will be blinded to the treatment assignment and the intraoperative anesthesia record showing the patient's core temperature. Only the preoperative and postoperative values of sCr will be necessary to adjudicate the Primary Outcome.

The study blind will be broken on completion of the clinical study and after the study database has been locked.

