At the end of LTx surgery, the ECD will be removed from the patient prior to emergence from general anesthesia, extubation, and/or transport to the ICU.

¹ The original protocol used a set point of 34.4 °C. However, we found that the core temperature dropped significantly (~0.5 °C) during the anhepatic phase (due to the cold liver graft and ice pack on the right kidney). Thus, we have modified the Set Point temperature to 34.8 °C.

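### Treated bradycardia regarded as typical at graft reperfusion is left out of the Section 5.3E arrhythmia count without an objective criterion, at a moment when the arms are planned to differ in temperature

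*Combined protocol and SAP*

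**What the plan says.** Section 5.3 item E lists the adverse events of special interest. One is intraoperative cardiac arrhythmia requiring treatment, "excluding bradycardia typically seen at the time of reperfusion of the liver graft". No heart rate, duration or degree of treatment separates a typical episode from one that counts.

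Four other parts of the plan bear on this:

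- **Temperature at reperfusion.** Section 4.1 says of the experimental arm: "Cooling will be initiated after induction of anesthesia and maintained throughout the anhepatic phase of LTx". Active rewarming follows: "Shortly (15 minutes) after the portal vein is reperfused, the ECD and other standard measures" are then used to warm the patient. Section 8.3 also places rewarming after portal reperfusion. In the control arm "the ECD and standard warming measures will be used to maintain normothermia throughout the operation".
- **Blinding.** Section 8.2: "No attempt will be made to blind the study doctors (anesthesiologists), who are investigators in the study, to the treatment assignment". The same section blinds "Research staff assigned to adjudicate the Primary Outcome", that is, AKI within 72 hours. No blinded review of adverse events is described.
- **Stopping rule.** Section 15.5.2 expects a combined incidence below 5% for grade 3 or 4 events from the 5.3E list, and stops the trial if grade 3 or 4 events exceed 10% overall or in either arm.
- **Other safety recording.** Section 11.1 defines an AE broadly, with no exclusion for reperfusion. Section 9.1.6 captures AEs throughout the study. Section 11.2.1 documents all SAEs whatever their relation to treatment. Section 5.3C records vasopressor totals by phase, including reperfusion.

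**The concern.** The protocol itself treats arrhythmia needing treatment as a safety outcome of this intervention, then removes one rhythm at one moment. That moment falls before rewarming begins, so the two arms are meant to be at different temperatures. If cooling altered how often reperfusion bradycardia needs treatment, the difference would sit inside the excluded category.

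A high background rate is not in itself a reason to exclude an event from a randomised comparison, because the control arm shows the background. With no criterion for what is typical and no blinded review, the label could also be applied differently in the two arms.

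At stake is the completeness of the safety comparison and of what the DSMB sees. The primary endpoint is not affected.

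**Working it through.** **1. Planned temperature gap at reperfusion (Sections 4.1 and 8.3).**
Smallest: 36.5 − 35 = 1.5 °C. Largest: 37.5 − 34 = 3.5 °C.
The footnote to Section 8.3 adds that, with the former set point, "we found that the core temperature dropped significantly (~0.5 °C) during the anhepatic phase". That is just before reperfusion. The set point has since been raised to 34.8 °C, so the 0.5 °C is not added to the gap here.

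**2. What the exclusion removes and what it leaves.**

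| Event | In the 5.3E arrhythmia item? |
|---|---|
| Treated bradycardia before or well after reperfusion | Yes |
| Treated non-bradycardic arrhythmia at reperfusion | Yes |
| Treated bradycardia at reperfusion judged not typical | Yes |
| Treated bradycardia at reperfusion judged typical | No |

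Only the last row is lost, but the line between the last two rows is undefined. The same list handles another common event differently: upper GI bleeding at device insertion is acknowledged as common and given a cut-off of more than 500 mL of blood return.

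**3. Would a comparison be informative if the event were recorded?** The documents give no rate of reperfusion bradycardia, so every rate below is an assumption. Sample size n = 101 per arm (Section 15.6), two-sided alpha 0.05.

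Test statistic: z = (x₁/n − x₂/n) / √[2p̄(1 − p̄)/n], with p̄ = (x₁ + x₂)/(2n). Exact power is the sum of the binomial probabilities of all pairs (x₁, x₂) with |z| > 1.96.

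Hand check for 10% v 25% by the normal approximation, with p̄ = 0.175:
Φ{[0.15 × √101 − 1.96 × √(2 × 0.175 × 0.825)] / √(0.10 × 0.90 + 0.25 × 0.75)} = Φ[(1.507 − 1.053)/0.527] = Φ(0.86) = 0.81, against 0.82 exact.

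| Assumed rates | Exact power, 101 per arm | Exact power, 115 per arm |
|---|---|---|
| 10% v 25% | 82% | 86% |
| 10% v 20% | 52% | 57% |
| 10% v 15% | 19% | 21% |
| 5% v 10% | 27% | 31% |
| 30% v 40% | 32% | 36% |

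Only a large excess would be detected reliably. Smaller ones would be visible as an estimate with an interval, but inconclusive.

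**4. Why the new line should not feed the 15.5.2 rule.** With 230/2 = 115 in an arm, more than 10% means at least 12 patients (0.10 × 115 = 11.5). The binomial chance of 12 or more at a single look is 1.3% if the true grade 3-4 rate is 5%, 48% at 10% and 94% at 15%. Suppose, as an assumption, that background reperfusion bradycardia of grade 3-4 added 5 to 10 points to a 5% rate. The chance of crossing in that arm would then rise from 1.3% to 48-94%, whether or not the arms differed. The 10% threshold was set against an expected rate of under 5% for the present list, so adding a background event to the count would change what the rule means.

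**The case against.** The strongest reply is that this is a narrow, symmetric exclusion of an expected event. It applies to both arms, covers one rhythm at one moment, and spares the list from routine events. Several parts of that reply stand:

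- **Who decides.** A reader might infer that the unblinded anesthesiologist decides what is typical. No section assigns that judgement. Section 8.2 says only that these doctors are unblinded, and Section 11.1 has the Investigator record AEs. The supportable statement is that no objective criterion and no blinded review are given.
- **When the arms differ.** A reader might infer that reperfusion is the only time of contrast. It is not: cooling starts after induction, the synopsis anticipates a median of 4-5 hours of hypothermia, and treated arrhythmias at other times are counted.
- **Whether events vanish altogether.** A reader might infer that these episodes go wholly unrecorded. The broad AE definition, SAE reporting and reperfusion-phase vasopressor totals could capture some of them.
- **Prior evidence.** Section 2.1 states that cardiovascular instability was not observed in a secondary analysis of the aneurysm-surgery trial or in the donor trial, and no passage links cooling to reperfusion bradycardia.

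These fallbacks do not close the gap. Nothing says whether an episode excluded by 5.3E is still an AE under 11.1. The method described in 11.1 is discussion with the subject, who is anesthetised at the time. The Visit 1 list in Section 10.1 has no AE step, and Appendix 1 marks adverse experiences only at Visit 2, although Section 9.1.6 says capture is continuous. SAE rules would reach life-threatening episodes but not necessarily every treated one. Vasopressor totals do not identify bradycardia, and Section 5.3C calls vasopressor use extremely common. The two reassuring studies do not involve graft reperfusion in a cooled liver recipient.

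**Conclusion.** The point holds in a limited form. A stated rule with an undefined term removes a possible between-arm difference from the 5.3E list, and from the 15.5.2 rule in so far as that rule counts the 5.3E events. Its second sentence does not repeat the reference to 5.3E, but reading the two sentences together is the natural course.

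The planned temperature gap of 1.5-3.5 °C comes directly from the documents. The power figures do not: they rest on assumed rates and show only that a large excess would be detectable if recorded. The documents contain no evidence that reperfusion bradycardia differs by arm or that anyone would apply the exclusion unevenly. A reader might go further and conclude that a harm of cooling is being hidden; nothing in the text supports that. Bias arises only if the frequency of the event, or its labelling as typical, differs between arms.

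This is a cheap improvement to the safety data. No efficacy analysis is affected.

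**What to change.** 1. In Section 5.3E, add a separate line for all bradycardia at graft reperfusion that required treatment, in both arms, taken from the anesthesia record. This removes the need to judge what is typical for that line.
2. Tabulate it by arm with the difference and a confidence interval, compare it by arm, and show it by arm to the DSMB.
3. State in Section 15.5.2 that this line stays outside the 10% count, so that the rule continues to apply to the events it covers now.
4. Reconcile 5.3E with 11.1: say whether a reperfusion episode excluded from the arrhythmia item is still recorded as an AE. Add an intraoperative AE entry at Visit 1 in Section 10.1 and Appendix 1, to agree with Section 9.1.6.

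The cost is one CRF field and a higher tabulated arrhythmia rate in both arms, which the report should explain. Clinical care does not change. Some subjectivity remains, because the decision to treat is still made by clinicians who know the arm.
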